**Table 4. Alignment of Visits Relative to Dose 3 between Vaccinated and Unvaccinated Participants on the 3-Dose Regimen**

Dose #	Unvaccinated SOT (3-doses)		Vaccinated SOT (3-doses)	
	(Visit # / Study Day)	Days Since Most Recent Dose	(Visit# / Study Day)	Days Since Most Recent Dose
Dose 1	Visit 1 / Day 1	0		
	Visit 2 / Day 8	7		
Dose 2	Visit 3 / Day 29	0		
	Visit 4 / Day 36	7		
Dose 3	Visit 5 / Day 57	28		
	Visit 6 / Day 85	0	Visit 1 / Day 1	0
	Visit 7 / Day 92	7	Visit 2 / Day 8	7
	Visit 8 / Day 113	28	Visit 3 / Day 29	28
	Visit 9 / Day 265	180	Visit 4 / Day 180	180
	Visit 10 / Day 450	365	Visit 5 / Day 365	365

### **9.3. Appendix C. Imputation Rules for Missing Prior/Concomitant Medications and Non-Study Vaccinations**

Imputation rules for missing or partial medication start/stop dates are defined below:

1. Missing or partial medication start date:

- If only Day is missing, use the first day of the month, unless:
  - The medication end date is after the date of first injection or is missing AND the start month and year of the medication coincide with the start month and year of the first injection. In this case, use the date of first injection
- If Day and Month are both missing, use the first day of the year, unless:
  - The medication end date is after the date of first injection or is missing AND the start year of the medication coincide with the start year of the first injection. In this case, use the date of first injection
- If Day, Month and Year are all missing, the date will not be imputed, but the medication will be treated as though it began prior to the first injection for purposes of determining if status as prior or concomitant.

Confidential

2. Missing or partial medication stop date:

- If only Day is missing, use the earliest date of (last day of the month, study completion, discontinuation from the study, or death).
- If Day and Month are both missing, use the earliest date of (last day of the year, study completion, discontinuation from the study, or death).
- If Day, Month and Year are all missing, the date will not be imputed, but the medication will be flagged as a continuing medication.

#### **9.4. Appendix D Imputation Rules for Missing AE dates**

Imputation rules for missing or partial AE start dates and stop dates are defined below:

1. Missing or partial AE start date:

- If only Day is missing, use the first day of the month, unless:
  - The AE end date is after the date of first injection or is missing AND the start month and year of the AE coincide with the start month and year of the first injection. In this case, use the date and time of first injection, even if time is collected.
- If Day and Month are both missing, use the first day of the year, unless:
  - The AE end date is after the date of first injection or is missing AND the start year of the AE coincides with the start year of the first injection. In this case, use the date of first injection
- If Day, Month and Year are all missing, the date will not be imputed. However, if the AE end date is prior to the date of first injection, then the AE will be considered a pre-treatment AE. Otherwise, the AE will be considered treatment-emergent.

2. Missing or partial AE end dates will not be imputed.

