17. Trained study site personnel will call all participants to collect information relating to any AEs, MAAEs, SAEs, AESIs, AEs leading to discontinuation from dosing and/or study participation withdrawal, information on concomitant medications associated with those events, and any nonstudy vaccinations. In addition, study personnel will collect information on known participant close contact exposure to someone with known COVID-19 or SARS-CoV-2 infection and on participant experience of COVID-19 symptoms.
18. All concomitant medications and nonstudy vaccinations will be recorded through 28 days after injection; all concomitant medications relevant to or for the treatment of an SAE, confirmed (biopsy-proven) or suspected events of organ transplant rejection, or MAAE will be recorded from Day 1 through the final visit (Day 365). In addition, the 2 previous doses of the Moderna COVID-19 vaccine will be recorded in the participant's eCRF regardless of the timing.
19. All immunosuppressant medications, for 3 months prior to Screening and throughout the study. Any change in the maintenance therapy should be recorded and the reason for the change documented.

Table 10: Booster Dose Phase (Part B: Group B2, Group B3, Group B4, and Group B5)

Visit Number	BD-1	BD-1a	BD-2	-	BD-3	-	BD-4
Type of Visit	C	C	C	SC	C	SC	C
Study Visit Day	BD-D1 ¹ (D205 for SOTr who received 3 doses; D120 for SOTr who received 1 dose; D149 for healthy cohort; at least 4 mos from last dose for SOTr who received primary series under EUA)	BD-D4	BD-D8	14 and 21 days after BD-D1 (BD-D15, BD-D22)	BD-D29	BD-D59, BD-D89, BD-D119, BD-149	BD-D181
Window Allowance (Days)	- 14 days	-2	+3	+3	-3/+14	+3	-3/+14
Days Since Most Recent Vaccination (in Part B)	0	3	7	-	28	-	180
Informed consent form, demographics, concomitant medications, medical history	X						
Review of inclusion and exclusion criteria	X						
Physical examination including height and weight ²	X				X		X
Lymph node assessment ³	X		X				
Vital signs ⁴	X		X		X		X
Pregnancy testing ⁵	X						
Immunogenicity Assessment							
Blood for immunologic analysis and assessment of Ab against nonvaccine antigen ⁶	X				X		X

Visit Number	BD-1	BD-1a	BD-2	-	BD-3	-	BD-4
Type of Visit	C	C	C	SC	C	SC	C

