## 4. Study Design

### 4.1. Overall Study Design

This is a Phase 3b, open-label study to evaluate the safety, reactogenicity, and immunogenicity of mRNA-1273 SARS-CoV-2 vaccine in SOT recipients and healthy controls. Adult kidney and liver transplant recipients and healthy control participants who are at least 18 years of age will be enrolled at ~20 sites in US and non-US sites.

Approximately 240 adult participants (220 previously vaccinated or unvaccinated participants who have had a kidney or liver transplant and 20 unvaccinated healthy adults) will be enrolled. At least 50 SOT recipients who completed primary series vaccines with mRNA or non-mRNA COVID-19 vaccine under EUA outside the study will be enrolled in Part B (Group B4).

[figure not shown]
In Part A, all SOT recipients who were unvaccinated prior to enrollment will receive 2 doses of 100  $\mu$ g of mRNA-1273 (vaccine) 28 days apart (window of -3/+7 days for the second dose) (Group A1). The SOT recipients will be offered the opportunity to receive a third dose of vaccine at Day 85 (window of -3/+7 days for the third dose) (Group A2). All healthy participants will receive 2 doses of vaccine 28 days apart (window of -3/+7 days for the second dose) (Group A5). SOT recipients who were previously vaccinated with 2 doses of Moderna COVID-19 vaccine under the EUA prior to enrollment will receive dose 3 on Day 1 (Group A3). These participants will be referred to as previously vaccinated throughout this document.

Under Amendment 4, unvaccinated SOT participants who will be enrolled will be given 3 100  $\mu$ g doses in Part A then proceed to Part B to receive a 100  $\mu$ g booster dose (Group A2 to Group B2). SOT participants previously vaccinated with 2 doses of Moderna COVID-19 vaccine outside of the study who will be enrolled will receive a third 100  $\mu$ g dose in Part A then proceed to Part B to receive a 100  $\mu$ g BD (Group A3 to Group B3). SOT participants who completed primary series vaccines with mRNA or non-mRNA COVID-19 vaccine outside of the study who consent to receive 1 booster dose in Part B (Group B4). Healthy participants who will be enrolled will be given 2 100  $\mu$ g doses in Part A then proceed to Part B to receive a 100  $\mu$ g booster dose (Group A5 to Group B5).

In Part B, all eligible active participants in Part A will be offered to receive a 100  $\mu$ g BD of mRNA-1273 who are at least 4 months from the last dose.

[figure not shown]

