**For calculation regarding antibody levels/concentrations**, antibody values reported as below LLOQ will be replaced by  $0.5 \times \text{LLOQ}$ . Values that are greater than the upper limit of quantification (ULOQ) will be used as available. Values that are reported as greater than ULOQ ( $>\text{ULOQ}$ ) without actual values will be replaced by ULOQ for analysis. Missing results will not be imputed, unless otherwise specified.

**The following Analysis Stages** will be defined for use in this study:

- Up to 28 days after any vaccination:

This stage starts at the day of each vaccination and continues through the earliest date of (the day of each vaccination and 27 subsequent days, next vaccination [if applicable]). This analysis period will be used as the primary analysis period for safety analyses (including unsolicited AEs), except for solicited ARs, unless specified otherwise.

- Throughout the study period:

For subjects in Part A, this analysis period starts at the first study injection on Day 1 and continues through the earliest date of study completion (or prior to BD), discontinuation from the study, or death.

For subjects in Part B, this analysis period starts at the BD on BD-Day 1 and continues through the earliest date of study completion, discontinuation from the study, or death.

For subjects in Part A and Part B, this analysis period starts at the first study injection on Day 1 and continues through the earliest date of study completion, discontinuation from the study, or death.

**Unscheduled visits:** Unscheduled visit measurements will be included in the analysis as follows:

- In scheduled visit windows per specified visit windowing rules.
- In the derivation of baseline/last on-treatment measurements.
- In the derivation of maximum/minimum on-treatment values and maximum/minimum change from baseline values for safety analyses.
- In individual subject data listings as appropriate.

**Visit windowing rules:** The analysis visit windows for protocol-defined visits are provided in [Appendix B](#). Results in previously vaccinated participants who received a third

Confidential

injection in the study will be presented in tables, figures, and listings at study visits related to the third injection.

**Incomplete/missing data** will be handled by the following conventions:

- Imputation rules for missing prior/concomitant medications, non-study vaccinations and procedures are provided in [Appendix C](#).

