### **6.3.1. Adverse Events**

Unsolicited AEs are collected for the purpose of assessing safety. All safety analyses will be based on the Safety Set.

A treatment-emergent AE (TEAE) is defined as any event occurring during the study not before exposure to study vaccine or any event already present that worsens after exposure to study vaccine. Worsening of a pre-existing condition after vaccination will be reported as a new AE.

Adverse events will also be evaluated by the investigator for the coexistence of MAAE which is defined as an AE that leads to an unscheduled visit to a healthcare practitioner.

Unsolicited AEs will be coded by PT and SOC using MedDRA and summarized by participant group and analysis stage (up to 28 days after any vaccination and throughout the study period from Day 1 (Part A)/BD-Day 1 (Part B)/Day 1 (Part A and Part B); see [Section 6.1](#) for definitions of participant group and analysis stage).

Similarly, adverse events related to organ rejection status will be reviewed by an adjudication committee as described in Section 7.6.1 of Protocol Amendment 4 to determine whether they represent an adjudicated biopsy-proven organ rejection. Events that are adjudicated as biopsy-proven organ rejection will be summarized for transplant recipients by participant group and analysis stage. Adjudication results will be listed.

All summary tables (except for the overall summary of AEs) for unsolicited AEs will be presented by SOC and PT for TEAEs with counts of subjects included. SOC will be displayed in internationally agreed order. PT will be displayed in descending order of frequency, overall, and then alphabetically within SOC. When summarizing the number and percentage of subjects with an event, subjects with multiple occurrences of the same AE or a continuing AE will be counted once. Subjects will be presented according to the highest severity (the strongest relationship) in the summaries by severity/grade (of related AEs), if subjects reported multiple events under the same SOC and/or PT.

Percentages will be based upon the number of subjects in the Safety Set within each participant group.

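### Partial adverse event dates are anchored to the first injection only, so a day-missing event after a Part B booster (Groups B2, B3, B5) or the Group A2 third dose can be dated before that dose and leave its 28-day safety window.

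*SAP*

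**What the plan says.** SAP Appendix D gives two rules for partial adverse event start dates.

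- Day missing: "If only Day is missing, use the first day of the month, unless" the event's end date is later than the first injection or missing, and "the start month and year of the AE coincide with the start month and year of the first injection". The first injection date is then used.
- Day and month missing: "If Day and Month are both missing, use the first day of the year, unless" the event's year is that of the first injection, with the same end-date condition.

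Neither rule mentions a second dose, third dose or booster, and no other SAP section adds an anchor for them.

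The imputed date decides where the event is counted. SAP Section 6.3.1 has unsolicited events "summarized by participant group and analysis stage". Section 6.1 makes the primary safety stage "the day of each vaccination and 27 subsequent days", cut short by the next vaccination. Its Part A period stops before the booster, and "For subjects in Part B, this analysis period starts at the BD on BD-Day 1". Section 3.1 lists unsolicited events through 28 days after the booster as a Part B primary safety endpoint.

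Section 6.1 also sends the reader to Appendix C for these rules, although they are in Appendix D.

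**The concern.** The exception in Appendix D stops an event in the month of the first dose from being dated before that dose. The study later gained a third dose and a booster, and the protection was not extended to them. Other parts of the SAP were: there is a pre-booster baseline, a study day counted from the booster, a Part B stage and booster visit windows.

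The resulting error runs one way. An event whose month matches the booster month, with an unknown day, is moved to before the booster even when its recorded end date lies after it. It then leaves the window used for a Part B primary safety endpoint. In small booster groups one or two events can alter a reported percentage.

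**Working it through.** The plan states no figure here to reproduce, so the check applies the rule as written.

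**Inputs**

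- Day-missing rule and its single exception: SAP Appendix D.
- Window of 28 days (vaccination day plus 27): SAP Section 6.1.
- Boosted participants from Part A are those "who are at least 4 months from the last dose" (SAP Section 4.1).
- Planned booster days: "D205 for SOTr who received 3 doses; D120 for SOTr who received 1 dose; D149 for healthy cohort" (Protocol Appendix 1, Table 10). These are Groups B2, B3 and B5.
- Assumptions, not in the documents: booster dates spread evenly over a 365-day year, true onset uniform over the 28 days, and end date missing or after the first injection.

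**Step 1: can the exception apply to these boosters?** No. The shortest planned interval from first injection to booster is 119 days (B3), or 105 using the 14-day early allowance in Table 10. The two cannot share a calendar month.

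**Step 2: how many events are affected?** For a booster on day *d* of a month of length *L*, the number of window days in the same month is min(28, L − d + 1). Summed over *d*:

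- 31-day month: 4 × 28 + (27 + … + 1) = 112 + 378 = 490
- 30-day month: 3 × 28 + 378 = 462
- 28-day month: 28 + 378 = 406

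Over a year: 7 × 490 + 4 × 462 + 406 = 5,684 of 365 × 28 = 10,220 booster-date and onset-day pairs, or 55.6%. Boosters on the 1st contribute 12 × 28 = 336, and there the imputed date equals the booster date. The rest are dated too early:

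- (5,684 − 336) / 5,684 = 94.1% of same-month events
- 5,348 / 10,220 = 52.3% of all day-missing events in the 28-day window

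The other 44.4% begin in the following month. They are dated to its first day, which is after the booster and still in the window.

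The imputed date precedes the booster by 10.5 days on average and by 30 at most.

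**Step 3: does the event fall in the previous dose's window instead?** The smallest distance from the previous dose to the imputed date is:

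- B2: 205 − 85 − 30 = 90 days
- B3: 120 − 1 − 30 = 89 days (75 with the 14-day allowance)
- B5: 149 − 29 − 30 = 90 days

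All exceed 27, so the event is in no 28-day window. Protocol Section 3.1.1 gives Day 129 for the healthy cohort's booster; that and Table 10 need reconciling, but 129 − 29 − 30 = 70 days gives the same answer.

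Example (B3): first injection 10 January 2022, booster 9 May 2022. An event recorded as May 2022 is imputed to 1 May 2022.

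**Step 4: the other doses**

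- *Group A2, dose 3* (Day 85, 56 days after dose 2). A backdated event lands in dose 2's window only if dose 3 was on the 30th or 31st. That is 7 × (2 + 1) + 4 × 1 = 25 of 5,348, so 99.5% leave the 28-day stage.
- *Dose 2 on schedule* (28 days after dose 1). Any backdating of a day or more lands in dose 1's window, so the event stays in the any-vaccination stage and only its attribution to a dose changes. At the +7-day limit it stays if dose 2 fell on the 9th or later: (7 × 276 + 4 × 253 + 210) / 5,348 = 3,154 / 5,348 = 59%.
- *Group B4 booster and Group A3 dose 3.* The footnotes to SAP Table 3 call these the first study injection, so the exception applies and 0% are dated before the dose.

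**The case against.** The strongest reply is that little changes in practice.

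- Solicited reactions come from daily eDiary entries.
- Time of onset is a required field for unsolicited events (Protocol Section 7.5.11).
- Booster recipients are contacted on BD-D4, D8, D15, D22 and D29 (Table 10).
- The documents give no rate of partial dates, and few are likely.

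This stands, and it keeps the point minor.

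Three stronger readings are tempting and are not supported.

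- *Every day-missing event in a booster month is misassigned.* Group B4, planned at 50 or more participants, is protected. Events that truly began earlier in the month are correctly placed before the booster.
- *The rule understates events after every later dose.* On-schedule dose 2 events remain in the 28-day stage, and the Group A3 third dose is covered by the exception.
- *Events disappear from safety reporting.* Treatment-emergent status depends on the first exposure, and the combined stage running from Day 1 to study end still counts them. What changes is the 28-day table and the split between Part A and Part B.

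None of this answers the mechanism for B2, B3 and B5 or for the A2 third dose.

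**Conclusion.** The point holds, as a minor one. For boosters in B2, B3 and B5, Appendix D as written dates about 94% of same-month, day-missing post-booster events before the booster. They leave the 28-day window and move to the Part A stage. For the A2 third dose nearly all backdated events likewise leave the 28-day window.

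The 94% depends on evenly spread booster dates and uniform onset. The direction depends on neither. It is a share of day-missing events, not of all events, and the number of affected events cannot be estimated from the documents.

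**What to change.** In the day-missing branch of SAP Appendix D:

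1. If any study injection (first, second, third or booster) was given in the event's start month and year, and the event's end date is missing or on or after the most recent of these, set the start date to that injection.
2. If the end date is before that injection, apply the same test to any earlier injection in the month.
3. Otherwise use the first of the month.

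An event that began after the booster cannot have ended before it, so the 94% falls to 0% in B2, B3 and B5. Group B4 stays at 0%.

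The cost is a few sentences and a small programming change. The downside is that some events that truly began earlier in the month will be dated to the booster, which is conservative for booster safety. Using on or after in place of after also means that a month-only event ending on the day of the first injection is dated to that day.

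Leave the year-only branch alone. Anchoring it to the latest injection of the year would move genuine Part A events into the post-booster window. Leave Appendix C alone too: a medication can be both prior and concomitant under SAP Section 6.2.5, so a start date moved to the 1st does not change its concomitant status.

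Correct the Section 6.1 cross-reference for adverse event dates from Appendix C to Appendix D.

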#### **9.5. Appendix E. Schedule of Events**

Refer to Table 7, Table 8, Table 9, and Table 18 in Appendix 1 (Schedule of Events) in Protocol Amendment 4.

Confidential

## 9.6. Appendix F. Severity Grading of Laboratory Abnormalities

**Table 5. Severity Grading of Laboratory Abnormalities**

Serum Chemistry a	Mild (Grade 1)	Moderate (Grade 2)	Severe (Grade 3)	Potentially Life-threatening (Grade 4) b
Creatinine (mg/dL)	1.5 – 1.7	1.8 – 2.0	2.1 – 2.5	> 2.5 or requires dialysis
ALP; increase by factor	1.1 – 2.0 × ULN	2.1 – 3.0 × ULN	3.1 – 10 × ULN	> 10 × ULN
Liver function tests – ALT and AST; increase by factor	1.1 – 2.5 × ULN	2.6 – 5.0 × ULN	5.1 – 10 × ULN	> 10 × ULN
Bilirubin – when accompanied by any increase in liver function test; increase by factor	1.1 – 1.25 × ULN	1.26 – 1.5 × ULN	1.51 – 1.75 × ULN	> 1.75 × ULN
Bilirubin – when liver function test is normal; increase by factor	1.1 – 1.5 × ULN	1.6 – 2.0 × ULN	2.0 – 3.0 × ULN	> 3.0 × ULN

Abbreviations: ALP = alkaline phosphatase; ALT = alanine aminotransferase; AST = aspartate aminotransferase; ULN = upper limit of the normal range.

- a The laboratory values provided in the tables serve as guidelines and are dependent upon institutional normal parameters. Institutional normal reference ranges should be provided to demonstrate that they are appropriate.
- b The clinical signs or symptoms associated with laboratory abnormalities might result in characterization of the laboratory abnormalities as potentially life-threatening (Grade 4). For example, a low sodium value that falls within a Grade 3 parameter (125 – 129 mEq/L) should be recorded as a Grade 4 hyponatremia event if the participant had a new seizure associated with the low sodium value.

Source: Guidance for industry – Toxicity Grading Scale for Healthy Adult and Adolescent Volunteers Enrolled in Preventive Vaccine Clinical Trials; tables for laboratory abnormalities ([DHHS 2007](#)).

**Table 6. Severity Grading of Vital Sign Abnormalities**

Vital Signs a	Mild (Grade 1)	Moderate (Grade 2)	Severe (Grade 3)	Potentially Life-threatening (Grade 4) b
Tachycardia (beats per minute)	101 – 115	116 – 130	> 130	ER visit or hospitalization for arrhythmia
Bradycardia (beats per minute) b	50 – 54	45 – 49	< 45	ER visit or hospitalization for arrhythmia
Hypertension (systolic) (mm Hg)	141 – 150	151 – 155	> 155	ER visit or hospitalization for malignant hypertension
Hypertension (diastolic) (mm Hg)	91 – 95	96 – 100	> 100	ER visit or hospitalization for malignant hypertension
Hypotension (systolic) (mm Hg)	85 – 89	80 – 84	< 80	ER visit or hospitalization for hypotensive shock
Respiratory rate (breaths per minute)	17 – 20	21 – 25	> 25	Intubation

Abbreviation: ER = emergency room.

Note that fever is classified under systemic reactions for grading purposes.

a Participant should be at rest for all vital sign measurements.

b When resting heart rate is between 60 – 100 beats per minute. Use clinical judgment when characterizing bradycardia among some healthy participant populations, for example, conditioned athletes.

Source: Guidance for industry – Toxicity Grading Scale for Healthy Adult and Adolescent Volunteers Enrolled in Preventative Vaccine Clinical Trials; tables for clinical abnormalities ([DHHS 2007](#)).

